Protocol Title: Use of Belatacept during Post Depletional Repopulation to Facilitate Tolerance in Renal Allograft Recipients

Investigator: [name]

Protocol Date: 10Jul2015

NCT Number: NCT00565773

SYNOPSIS

| |
|-----------------------------------------------------------------------------------------------------------------------------------------------------------------------------------------------------------------------------------------------------------------------------------------------------------------------------------------------------------------------------------------------------------------------------------------------------------------------------|
| Title of Study: Use of Belatacept During Post Depletional Repopulation to Facilitate Tolerance in Renal Allograft Recipients |
| Study Phase: II |
| IND Sponsor: [name] PhD |
| Participating Site: Emory University |
| Study Design: Single-center, open-label, proof-of-concept study in non-HLA-identical live and deceased donor renal transplants. |
| Duration of Study: Subjects will be enrolled over a one-year period and followed for up to five years. |
| Number of Subjects: Approximately 40 |
| Study Population: Adult, EBV seropositive patients who do not have evidence of DSA pretransplant and who are scheduled to receive a kidney transplant at Emory University. Candidacy for transplantation will be determined using the standard methods of evaluation active at Emory during the study period. |
| Primary Objective: To determine whether lymphocyte depletion with alemtuzumab followed by belatacept and sirolimus will permit renal allograft function without rejection, and will allow for a general population of renal transplant recipients to be weaned to belatacept monotherapy for maintenance immunosuppression. The primary endpoint will be the number of patients successfully withdrawn from sirolimus for 1 year after their last dose of sirolimus. |

Secondary Objectives:

- 1) Determination of the prognostic ability of assays based on surface phenotype changes seen during homeostatic repopulation, including Ki67 expression, T_{REG} and B_{TRANS} cell surface phenotypes, and T_M to T_{REG}/B_{TRANS} balance, with regard to the anticipation of successful immunosuppressive drug withdrawal.
- 2) Assessment of the proposed therapies to prevent biopsy proven acute rejection at 1, 3 and 5 years post-transplant compared to the standard reported in the SRTR database for similar patients.

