indicates to us that complete immunosuppressive weaning offers an unacceptable risk and we have accordingly altered our protocol to eliminate this as an explicit goal of the trial. It is important to point out that our approach in this situation is substantially different from that taken by the investigators of a recently reported tolerance trial.^{2,109-111} In this trial performed at the Massachusetts General Hospital (MGH), several patients have been weaned from all immunosuppression. However, ABMR led to graft loss in 2 of 10 patients, and DSA formed in several other patients that have been followed expectantly. Endothelial injury has been observed in many patients. From a statistical standpoint, it is not clear if the results from our regimen differ from those of this trial, as we have not pressed forward aggressively to continue pursuing a drug-free state in the face of an asymptomatic DSA. We have viewed the appearance of DSA as an unacceptable risk for late graft loss that should be avoided, and opted not to consider immunosuppression elimination without some evidence that monotherapy belatacept has some risk. We reason that the ultimate goal is graft function without side effects, and that risking graft loss in pursuit of an immunosuppressive-free state without evident benefit over a state maintained with a once monthly CoB-based regimen imposes risk without compensatory benefit. Particularly in the absence of a clear metric identifying patients at risk for ABMR and graft loss, we view complete drug withdrawal to be unsupportable at this time.

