2 STUDY OBJECTIVES

2.1 Primary Objective

This study will determine whether T-cell depletion followed by belatacept and daily maintenance therapy with sirolimus will permit recipients of renal allografts to avoid rejection and eventually be weaned to belatacept monotherapy maintenance immunosuppression. The primary endpoint will be the number of patients successfully withdrawn from sirolimus for 1 year after their last dose of sirolimus. “Successfully withdrawn” will be defined as a patient off sirolimus without clinical or biopsy evidence of rejection.

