3.4 Sample Size Determination

Our prior experience with alemtuzumab, belatacept and sirolimus, in recipients of live donor kidneys suggests that this regimen is very effective in preventing acute rejection, with only one steroid sensitive, clinical rejection episode seen in the first year. However, with the liberalization of the inclusion criteria, it is anticipated that an acute rejection rate prior to initiation of sirolimus withdrawal of up to 20% will exist, excluding up to four patients from eligibility for sirolimus withdrawal. It also is anticipated that four additional patients will either not meet other criteria for withdrawal or will refuse to be withdrawn from immunosuppression. The number of patients has therefore been chosen to have approximately 12 patients who are eligible for sirolimus withdrawal and in whom withdrawal is attempted, in order to establish a reasonable proof-of-concept. This target of 12 subjects in whom sirolimus withdrawal is attempted will allow for the detection approximately 6 subjects successfully withdrawn from sirolimus for one year, assuming the probability of a subject in whom withdrawal is attempted being successfully withdrawn from sirolimus for one year is 50%, a rate determined by the current cohort. Since there are no trials exploring monotherapy belatacept reported in the literature or registered with ClinicalTrials.gov, this cohort of patients withdrawn successfully will represent a significant finding.

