4.2 Analyses

Demographics and Baseline Characteristics

Demographic and baseline characteristics of patients will be summarized descriptively by treatment group, by means and standard deviations (SDs) for continuous variables and frequency distribution for categorical variables. Summaries will be performed based on the data set.

Efficacy Analyses

No formal statistical hypothesis testing will be performed for the primary endpoint. All efficacy analyses will generally be descriptive in nature. The primary efficacy analysis will be to assess the proportion of patients successfully withdrawn from sirolimus for one year. The point estimate of this proportion and the exact two-sided 95% confidence interval (CI) will be provided for each treatment group. A patient will be considered to be successfully withdrawn from immunosuppression for one year if the patient has been administered only belatacept for a period of 365 days, following successful completion of sirolimus, and has not experienced biopsy-proven acute rejection, formation of DSA, or graft loss for this same period of 365 days. Secondary efficacy outcome measures involving incidences and proportions will be descriptively summarized with point estimates and exact, two-sided 95% CIs by treatment group. Other secondary efficacy outcome measures will be descriptively summarized by means and SDs for continuous outcomes and frequency distributions for categorical outcomes.

Safety Analyses

All AEs and SAEs will be summarized by treatment group. Laboratory values will also be descriptively summarized.

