6.2 Maintenance Immunosuppressive Reduction

Beginning any time after year 1 (week 53), participants who are deemed eligible for sirolimus withdrawal as determined by clinical and flow cytometric parameters

(described below) may be withdrawn from sirolimus. Withdrawal will proceed at a maximum rate of 66% of the original dose for 4 weeks, 33% of the original dose for another 4 weeks, then discontinued. However, each reduction in dose will be predicated on stable flow cytometric profile.

Criteria for Sirolimus Withdrawal. Participants will be deemed eligible for withdrawal of sirolimus if they meet all of the following criteria:

1. No episodes of steroid resistant acute rejection since transplant, and no episodes of steroid sensitive rejection for 12 months.
2. Stable renal function, as defined by both of the following:
 - a. GFR, using calculated CrCl (Cockcroft-Gault) of > 40ml/min.
 - b. Creatinine, which in the 12 weeks preceding withdrawal has not increased more than 20% with respect to the lowest creatinine observed during the same period.
 - c. Absence of histologic evidence of acute or chronic rejection on pre-withdrawal renal biopsy according to the Banff criteria for acute, chronic and humoral rejection.
3. Absence of DSA reactivity, as measured by de novo anti-donor-HLA antibodies.
4. ALC at least 80% of the baseline ALC prior to alemtuzumab.
5. Ki67 expression on CD3+ T cells that is within 1 standard deviation of the normal expression in untreated controls. Ki67 is typically seen in <3% of lymphocytes in health controls and a value >5% exceeds the value accepted for purposes of this trial.

For determining eligibility, a renal biopsy will be obtained and creatinine clearance will be estimated. Requisite blood samples will be obtained within two weeks before starting sirolimus withdrawal. Results of laboratory assessments of immune status will be made available to, and reviewed by, the investigator. These data will be reviewed with the knowledge of previous results of immunosuppression withdrawal obtained in the current trial up to the time of review.

Maintenance Immunosuppressive Therapy

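### Sections 2.1 and 4.2 define success on the primary endpoint differently, and no available text says which definition governs

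*Combined protocol and SAP*

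**What the plan says.** Section 2.1 makes the primary endpoint the number of patients successfully withdrawn from sirolimus for one year after the last dose. It then defines the term: success "will be defined as a patient off sirolimus without clinical or biopsy evidence of rejection". It mentions neither DSA nor graft loss, does not require that belatacept be the only drug, and does not refer to Section 4.2.

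Section 4.2 describes the primary efficacy analysis as the proportion successfully withdrawn from sirolimus for one year, reported with an exact two-sided 95% CI and no hypothesis test. It counts a patient as a success if "the patient has been administered only belatacept for a period of 365 days" after sirolimus has ended and the patient "has not experienced biopsy-proven acute rejection, formation of DSA, or graft loss for this same period of 365 days". It labels this state withdrawal from immunosuppression, although the patient is still on belatacept and the endpoint is withdrawal from sirolimus.

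The synopsis and Sections 3.3 and 3.4 use the term without defining it. Section 3.3 lists alloantibody formation as an item separate from the withdrawal endpoint. Section 3.4 plans for about 12 withdrawal attempts and "approximately 6 subjects successfully withdrawn from sirolimus for one year", but does not say under which definition its 50% planning rate was counted.

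**The concern.** Both sections are current text, both define the same endpoint, and they do not classify the same patients as successes. The primary result is a single descriptive proportion from a small, open-label, single-arm study, so the classification rule is in effect the result. While two rules stand, the choice between them could be made after the DSA results are known.

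The DSA case matters most to the meaning of the endpoint. In explaining why complete drug withdrawal was dropped, Section 1.3.5 says: "We have viewed the appearance of DSA as an unacceptable risk for late graft loss that should be avoided". Section 6.2 makes "Absence of DSA reactivity, as measured by de novo anti-donor-HLA antibodies" a condition for starting withdrawal. Under 2.1, a patient who develops that event during the year would still be reported as successfully withdrawn.

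**Working it through.** **1. The two definitions side by side**

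| Patient during the 365 days | Section 2.1 | Section 4.2 |
|---|---|---|
| (a) Belatacept alone, working graft, no rejection, new DSA | Success | Failure |
| (b) Switched from sirolimus to MMF, no rejection, still on MMF | Success, read literally | Failure (not belatacept alone) |
| (c) Graft loss without rejection | Success, read literally | Failure |
| (d) Non-acute rejection on biopsy, no DSA, no added drug | Failure only if rejection in 2.1 includes chronic rejection | Success |
| (e) Rejection treated with added drugs | Failure | Failure |

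- Case (a): Appendix A lists the clinical signs of rejection (fever, graft swelling or tenderness, creatinine rise, oliguria, imaging findings). DSA is not among them, so 2.1 cannot be read as covering DSA alone. The 6.2 criterion applies before weaning and does not classify DSA that appears afterwards.
- Case (b): Section 6.1 provides for conversion to MMF and prednisone on sirolimus intolerance. Section 1.3.5 reports that four of the first 20 patients were converted to MMF. It does not say in the available text how many of them stayed on MMF, rejection-free, for a year.
- Case (c): the literal reading of 2.1 sits badly with the synopsis aim that the regimen "will permit renal allograft function without rejection".
- Case (d) runs the other way. If it applies, neither definition is simply the stricter one.
- Case (e) is not discordant. Treatment under Sections 6.2, 6.6 and 9.2 adds or changes drugs, which breaks the belatacept-only condition.

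**2. The plan's own figures**

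Inputs: 20 enrolled (Section 3.1); up to 20% lost to acute rejection before withdrawal, four more lost for other reasons, 50% success (Section 3.4).

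- Rejection: 20 × 0.20 = 4.
- Attempts: 20 − 4 − 4 = 12.
- Expected successes: 12 × 0.50 = 6.

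These reproduce the stated 12 and 6.

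**3. Effect of discordant patients**

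Suppose six patients succeed under 2.1 and k of them fail 4.2. The proportion under 4.2 is (6 − k)/n. The exact (Clopper-Pearson) limits for x successes in n are the 2.5% quantile of Beta(x, n − x + 1) and the 97.5% quantile of Beta(x + 1, n − x).

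Two denominators are shown. Section 3.4 plans on 12 attempts. Section 4.1 assigns all efficacy analyses to all transplanted patients and treats attempted against not attempted as subgroups; with the enrolment in Section 3.1, that implies 20.

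| k | n = 12 | n = 20 |
|---|---|---|
| 0 | 6/12 = 50.0% (21.1–78.9) | 6/20 = 30.0% (11.9–54.3) |
| 1 | 5/12 = 41.7% (15.2–72.3) | 5/20 = 25.0% (8.7–49.1) |
| 2 | 4/12 = 33.3% (9.9–65.1) | 4/20 = 20.0% (5.7–43.7) |

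Per patient the shift is 1/12 = 8.3 points or 1/20 = 5.0 points. If the roughly 40 subjects in the synopsis were the denominator, it would be 1/40 = 2.5 points. The values of k are illustrative.

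**The case against.** The strongest reply is that 4.2 plainly governs. It sits inside the primary efficacy analysis, is the more detailed text, and is what an analyst following Section 4 would apply; 2.1 is a statement of objective. There is also no test, no interim analysis and no success threshold that a changed count could cross. The intervals in the table overlap heavily, and alloantibody formation would be evaluated under Section 3.3 in any case. This lowers the severity. It does not remove the conflict, because 2.1 gives its own definition directly after naming the endpoint and neither section defers to the other.

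A second reply is that the DSA statement in Section 1.3.5 explains why complete drug elimination was abandoned and does not define success on belatacept monotherapy, and that 6.2 concerns eligibility. That is correct. Both passages show which definition fits the sponsor's reasoning; neither settles which one applies.

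A reader might go further and infer that the two sections will probably report different counts. The documents do not support that. The available text gives no DSA frequency for this regimen, and part of the first-cohort results in Section 1.3.5 was not available to this review. A patient with DSA who restarted sirolimus within the year would also fail both definitions.

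A reader might also infer from the 6.2 entry criterion, "Absence of histologic evidence of acute or chronic rejection on pre-withdrawal renal biopsy", that chronic rejection must count as failure. That criterion governs the start of withdrawal. Section 4.2 contains no such component, and adding one is a design choice for the sponsor.

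**Conclusion.** The contradiction stands on the wording alone and needs no assumed event rate. Cases (a), (b) and (c) are successes under 2.1 and failures under 4.2, with (b) and (c) resting on a literal reading of 2.1. Case (d) may go the other way, depending on what rejection means in 2.1.

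The size is 8.3 points per discordant patient on 12 attempts, or 5.0 points on 20 transplanted patients. These figures assume the planned six successes under 2.1. The 12-patient figure suits cases (a) and (c) best, since a patient switched to MMF may never enter a sirolimus withdrawal attempt. The number of discordant patients cannot be predicted from the available text.

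It would be too strong to say that the primary endpoint has no usable definition, or that the reported rate is bound to be inflated: 4.2 is workable as it stands and most readers would presume that it applies. This should be fixed, and it does not invalidate the design.

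**What to change.** Use one definition throughout.

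- In Section 2.1, replace the sentence that defines successful withdrawal with a reference to the 4.2 definition. That definition matches the monotherapy aim and the sponsor's stated view of DSA.
- In Section 4.2, label the defined state as successful withdrawal from sirolimus, in place of withdrawal from immunosuppression.
- State whether biopsy evidence of chronic rejection counts as failure. Either answer is workable if it is fixed in advance.
- Report the count under the present 2.1 wording as a labelled sensitivity analysis.

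The cost is a few wording edits and one extra line in the results. No samples or visits are added: the flow chart in Section 8.1 already has a yearly anti-donor antibody test, and Section 9.2 already plans a biopsy one year after weaning. The reported success rate may be slightly lower than under 2.1. Clinical management is unaffected.

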2.2 Secondary Objectives

1. Determination of the prognostic ability of assays based on surface phenotype changes seen during homeostatic repopulation, including Ki67 expression, T_{REG} and B_{TRANS} cell surface phenotypes, and T_M to T_{REG}/B_{TRANS} balance, with regard to the anticipation of successful immunosuppressive drug withdrawal.
2. Assessment of the proposed therapies to prevent biopsy proven acute rejection at 1, 3 and 5 years post-transplant compared to the standard reported in the SRTR database for similar patients;
3. Assessment of the incidence of biopsy proven chronic allograft nephropathy at 1, 3 and 5 years post-transplant compared to that reported in the SRTR database for similar patients;
4. Assessment of the composite of occurrence of malignancies, and opportunistic infections by 1, 3 and 5 years compared to that reported in the SRTR database for similar patients;
5. Long term assessment of donor-specific immune responsiveness after prolonged therapy with belatacept (with or without sirolimus), and during and following drug

- withdrawal as determined by in vitro alloresponsiveness in CFSE mixed lymphocyte reactivity and ICCS;
6. Characterization of the repopulating immune system with regard to cell surface phenotype using MFC compared to prior experience with alemtuzumab alone or combined with other related regimens; and,
 7. Comparison of the function and survival of allografts transplanted using this protocol to historical controls transplanted using conventional immunosuppression to establish an initial assessment of this approach in a general transplant population.

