3.3 Criteria for Evaluation

1. Number of patients successfully withdrawn from sirolimus for 12 months after last dose of sirolimus
2. Biopsy proven acute rejection or chronic allograft nephropathy by 1, 3 and 5 years
3. Evidence of donor-specific hyporesponsiveness by MLR and ICCS
4. Evidence of regulatory T cell and transitional B cell activity in the periphery and allograft
5. Donor specific and third party alloantibody formation

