| BK viremia/viruria PCR | | X | | | X |
| Adverse Events | X | X | | | X |
| QoL | | | | X | |
| Neurologic Exam | | | X | | |
| Immunogenicity | | | | X ^a | |

^a These are specific study related assays for reporting purposes.

Long-Term Follow-Up Cohort 1

| Tests / Evaluations | Every 6months | Yearly |
|----------------------------------------------------------------------|----------------------|----------------|
| Telephone Reporting | X | |
| Serum Chemistry/ lipids /CBC | X | |
| Sirolimus trough | | X |
| Lymphocyte subsets | X | |
| Peripheral transcription | | X |
| CMV and EBV PCR | X | |
| BK viremia/viruria PCR | X | |
| PRA | | X |
| Anti-Donor Antibody | | X |
| Donor-specific and third party mixed lymphocyte responsiveness/ ICCS | | X |
| Renal Biopsy | | X ^b |
| Intragraft mRNA Analysis | | X ^b |
| Adverse Events | X | X |
| QoL | X | |
| Neurologic Exam | X | |
| PK | | |
| Immunogenicity | X | |

=

^b To be performed prior to weaning patient to monotherapy (generally at 12 months) and again after stable on monotherapy as clinically indicated.

Long-Term Follow-Up Cohort 2

| Tests / Evaluations | Monthly after Year 1 | Every 3 months from 6 - 24Months | Every 6 months | Yearly |
|----------------------------------------------------------------------|-----------------------------|-----------------------------------------|-----------------------|----------------|
| Telephone Reporting | | | X | |
| Serum Chemistry/ lipids /CBC | X ^c | | X | |
| Sirolimus trough ^d | X | | | X |
| Lymphocyte subsets Ki67 | | | X | |
| Peripheral transcription | | | | X |
| CMV and EBV PCR | | X | X | |
| BK viremia/viruria PCR | | X | X | |
| PRA | | | | X |
| Anti-Donor Antibody | | | | X |
| Donor-specific and third party mixed lymphocyte responsiveness/ ICCS | | | | X |
| Renal Biopsy | | | | X ^b |
| Intra-graft mRNA Analysis | | | | X ^b |
| Adverse Events | X ^e | | | |
| QoL | | | X | |
| Neurologic Exam | | | X | |
| Immunogenicity | | | X | |

^cStudy participants may have these labs drawn more or less frequently as deemed clinical necessary by the investigator.

^dStudy participants who are not weaning sirolimus and are on a stable, low dose can have trough levels monitored as frequently as a monthly basis or as clinically indicated.

^eIf study participant is on a stable dose of sirolimus, not weaning, and receiving commercial belatacept as an outpatient, then adverse events may be assessed every three months.

Year 1 Medication Flowchart

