9.2 Post-transplant Monitoring

Post-transplant Blood Monitoring. In general, functional monitoring will proceed in keeping with the standard of care for kidney transplantation at the Emory Transplant Center. Blood for testing of renal function (creatinine, BUN, hemoglobin/hematocrit) and electrolytes (including sodium, potassium, chloride, bicarbonate, magnesium, calcium and phosphorous) will be drawn daily until discharge and at least two times weekly for one month. Patients will be monitored weekly for at least 3 months or until the ALC exceeds 500 cells/mm³, whichever is longer. Thereafter, renal function will be assessed at least every two weeks until they reach their one-year evaluation. Lymphocyte repopulation and specific Ki67 and T_{REG} and B_{TRANS} phenotypes will be assessed monthly until 1 year after sirolimus elimination, and then every 3 months through 5 years by analysis of 7ml of heparinized blood by flow cytometry.

Biopsy Monitoring. A protocol biopsy will be performed following allograft reperfusion. Additional protocol biopsies will be performed at 6 months, and when the criteria for weaning to monotherapy belatacept are met (generally this will be during the second post transplant year) and again when the patient has been weaned to monotherapy belatacept for three months. An additional biopsy will be performed one year after weaning off sirolimus. It is assumed that histological acute allograft rejection is indicative of under-immunosuppression. Since histological rejection has been documented to occur in the absence of clinical renal dysfunction (so-called sub-clinical rejection) in up to 30% of persons with stable allograft function, it is reasonable to assume that some patients studied in this trial will have sub-clinical rejection, and thus be inappropriate for further immunosuppressive reduction. Protocol biopsies are thus clinically indicated to pre-empt inappropriate immunosuppressive weaning, as well as to detect other occult pathology

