known to arise in transplanted kidneys that could confound the interpretation of the study.¹³³⁻¹³⁴ In the event that subclinical rejection is detected, the patient will receive anti-rejection therapy in keeping with the standard of care, generally an oral steroid taper over 30 days and reevaluation of the patient's need for chronic immunosuppression. A follow-up biopsy will be performed in 3 months to assess resolution of subclinical rejection. Subclinical rejection, once resolved, will not in and of itself remove the patient from consideration of weaning, if it occurs during a period of homeostatic repopulation.

Renal biopsies also will be performed if any sustained rise in serum creatinine of greater than or equal to 30% of the baseline creatinine is detected. Baseline creatinine will be defined as the mean of five stable serum creatinine values within the first three months post-transplant. Stable is defined as a variance of +/- 20% or less of any value. Clinical suspicion of allograft pathology based on other grounds (urine cytology, pyuria, proteinuria, etc.) also will be considered grounds for biopsy at the discretion of the attending physician. An attending transplant physician or surgeon will perform all biopsies. The risks of transplant kidney biopsy will be included in the informed consent process for the protocol. At the time of each biopsy (protocol or clinically indicated), blood will be drawn for peripheral phenotyping and lymphocyte harvest (50ml heparinized).

Patients will be evaluated for cellular alloreactivity, donor-specific hyporesponsiveness and viral specific responsiveness pre-operatively, at the time that sirolimus withdrawal commences, 3 months after sirolimus withdrawal, at the time of clinical rejections, and at study termination. This will require 50ml of heparinized blood to be drawn at these time points and cryopreserved for analysis.

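### The SRTR comparison of biopsy-proven rejection and CAN does not say whether protocol-biopsy findings count, and 6.8 ends study participation for the same reasons that stop belatacept in 6.4

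*Combined protocol and SAP*

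**What the plan says.** **Outcome and comparator.** Section 2.2 wants the regimen's ability to "prevent biopsy proven acute rejection at 1, 3 and 5 years post-transplant compared to the standard reported in the SRTR database", and the same for biopsy-proven CAN. Section 3.3 lists the criterion as "Biopsy proven acute rejection or chronic allograft nephropathy by 1, 3 and 5 years". Section 4.2 gives secondary proportions a point estimate and an exact 95% interval. It has no rule on biopsy type, on matching to SRTR or on missing outcomes.

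**Biopsies.** Section 9.2 has a reperfusion biopsy and then: "Additional protocol biopsies will be performed at 6 months, and when the criteria for weaning to monotherapy belatacept are met". It adds biopsies at three months on belatacept monotherapy and one year after weaning, plus for-cause biopsies on a sustained creatinine rise of at least 30% or other clinical suspicion. It notes that sub-clinical rejection is found "in up to 30% of persons with stable allograft function" and expects some here. When it is found, "A follow-up biopsy will be performed in 3 months to assess resolution of subclinical rejection". In 8.1, the long-term tables put renal biopsy in the yearly column, with a footnote b that calls for it before weaning (generally at 12 months) and "again after stable on monotherapy as clinically indicated".

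**Follow-up.** Section 3.1 promises at least five years. Section 6.4 lists six reasons for stopping belatacept. Section 6.8 lists the same six as reasons for removal from the study. Both close with 8 weeks of safety follow-up for anyone discontinued from study therapy. Section 11.6 keeps death, graft loss, malignancy, PTLD and serious infection to the end of the study, for randomized subjects.

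**The concern.** A biopsy-proven rate depends on how often, and in whom, biopsies are done. Patients here have surveillance biopsies, and those who progress through weaning have more of them. If the SRTR figure rests on a different mix of biopsies, the comparison mixes the effect of the regimen with the intensity of looking. Two analysts could also report different rates from the same data, because the plan does not say which findings are events.

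The removal rule raises a second problem for the same objectives. Someone taken out of the study for an adverse event has no planned year-3 or year-5 rejection, CAN or graft-function status, yet belongs to the all-transplanted efficacy set in 4.1. The reason for removal may be related to outcome, so those missing values cannot be assumed to be harmless.

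**Working it through.** **1. The documents' own ratio.** Appendix C says biopsy-proven rejection was two to four times as frequent as the clinically suspected and biopsy-proven kind. From Table 1.3.4.3A at month 6 (any biopsy-proven / clinically suspected):
- more intensive (MI): 11/5 = 2.20
- less intensive (LI): 17/4 = 4.25
- cyclosporine: 13/6 = 2.17

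The statement reproduces.

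**2. Gap between definitions in the same patients.** Section 1.3.4 calls the MI regimen the closest to this trial. Gap = (any biopsy-proven − clinically suspected) / N.
- Month 6: 11/74 − 5/74 = 14.9% − 6.8% = 6/74 = 8.1 points.
- Month 12: 14/74 − 5/74 = 18.9% − 6.8% = 9/74 = 12.2 points (the table's footnote a gives the same clinically suspected counts at month 12).

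Month 6 is the safer illustration. MI patients were reallocated on Day 169 to 4- or 8-weekly dosing, and Appendix C links 8-weekly dosing with more sub-clinical rejection. The present trial doses every 4 weeks.

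**3. Does that split carry over?** Not directly. Clinically suspected rejection there required a creatinine rise of at least 0.5 mg/dL. Here a 30% rise triggers biopsy. Taking cohort 1's mean of 1.1 mg/dL (1.3.5) as an assumed baseline, 0.30 × 1.1 = 0.33 mg/dL. Some episodes classed as sub-clinical there would be for-cause here. Background drugs also differ.

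**4. CAN.** Appendix C gives MI month-12 CAN as 15/74 = 20.3% over all subjects, and 29% among those with at least one post-baseline biopsy. This rate, too, depends on who is biopsied.

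**5. Schedules side by side.** All patients have the 6-month biopsy. For weaning, 6.2 states: "For determining eligibility, a renal biopsy will be obtained and creatinine clearance will be estimated". After weaning, 9.2 fixes two further biopsies, while footnote b in 8.1 makes them depend on clinical indication although the entry sits in the yearly column. The number of surveillance biopsies in weaned patients is therefore not determined.

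**6. Who is lost under 6.8.**
- Withdrawn consent and detention: legitimate limits on follow-up.
- 56 days of dialysis with a functionally lost graft: the graft loss is already reported under 11.6.
- Adverse event or illness, pregnancy, two missed infusions: rejection, CAN and graft function are lost.
- Others discontinued from study therapy, such as after steroid-resistant rejection (6.6): the closing sentence of 6.8 states only 8 weeks for them. Their rejection is already recorded; later CAN and graft function are what is at risk.

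With x events seen and k subjects removed event-free, the rate lies between x/N and (x + k)/N, a width of k/N. For k = 1 this is 1/20 = 5 points in the current cohort (3.1), or 1/40 = 2.5 points over both cohorts (synopsis, approximately 40). The documents give no basis for k.

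**The case against.** On a plain reading, biopsy-proven means any positive biopsy, and Appendix C uses the term that way. Section 9.2 does give indications for biopsy. That stands: the plan has biopsy rules. What it lacks is a statement of which findings count against SRTR, and of the SRTR definition. Appendix C describes another study and does not settle this.

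Section 9.2 itself calls protocol biopsies clinically indicated, which softens the conflict with footnote b. But 7.9 and 9.2 also treat the two as different kinds of biopsy, so the passages still need reconciling.

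A reader might add the 30% in 9.2 to the pre-weaning rejection rate of up to 20% in 3.4 and forecast a much higher all-biopsy rate for this cohort. The documents do not support that. Both figures are ceilings, and the 20% may already include sub-clinical cases. Criterion 2c in 6.2 requires a pre-withdrawal biopsy free of histologic rejection, and 9.2 calls such patients unsuitable for further reduction. It does also say "Subclinical rejection, once resolved, will not in and of itself remove the patient from consideration of weaning", but only for rejection during homeostatic repopulation. A reader might likewise total the biopsies under each schedule; the yearly column in 8.1 makes such totals insecure.

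On follow-up, the synopsis says up to five years, and missed infusions carry a medical-monitor exception. Both narrow the conflict without removing it, since five-year results are still an objective. A reader might also infer from the word randomized in 4.1 and 11.6 that the current, non-randomized cohort has no efficacy set and no continued event reporting. Carry-over from cohort 1, which was randomized to donor marrow or none, is the likelier explanation. It needs only a wording correction.

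**Conclusion.** Both parts hold, at moderate weight. The SRTR comparison for objectives 2 and 3 lacks an event definition tied to biopsy indication and a matching SRTR definition. In the nearest arm that the protocol reports, the choice of definition moved the rate by 8.1 points at month 6. This is an illustration, not a forecast for this trial. How SRTR ascertains rejection and CAN is not in the documents, so a claim that the comparison favors or penalizes the regimen would be unsupported.

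Section 6.8 contradicts 3.1 and 4.1 for rejection, CAN and graft function, mainly for removals due to adverse event or illness, pregnancy and missed infusions. The number affected is unknown and may be small; all cohort 1 patients tolerated belatacept (1.3.5). These analyses are secondary and descriptive, so no stated power or sample size is affected.

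**What to change.** **Biopsy definition (2.2, 3.3, 4.2).** Record each biopsy as protocol or for cause. Report rejection and CAN both ways, for-cause and all-biopsy, at 1, 3 and 5 years. State the SRTR definition used and set it against the rate that matches. Note that treating sub-clinical episodes may lower the for-cause rate.

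**Biopsy schedule (8.1, 9.2).** Reconcile the yearly entry and footnote b with the fixed post-weaning biopsies in 9.2.

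**Follow-up (6.8 with 3.1, 4.1, 11.6).** Separate stopping study drug from leaving the study, so that the first does not end outcome follow-up. Collect annual status to year 5 from routine records for rejection, CAN on clinically indicated biopsy, and graft function, except where consent is withdrawn or research follow-up of a detained subject is not permitted.

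**Wording.** In 4.1 delete *randomized and*. In 11.6 replace *randomized* with *transplanted*.

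**Cost.** One data field per biopsy (9.2 already draws the distinction), a few sentences of text, and annual status on a few patients at one center whose database already holds graft function and the post-transplant course (4.1).
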